6. STATISTICAL METHODS AND DETERMINATION OF SAMPLE SIZE

6.1 Statistical evaluation – general aspects

A comprehensive Statistical Analysis Plan (SAP) for the analyses involving Part 2 data (ie post randomisation data) will be prepared before unblinding of the data.

The robustness of results with respect to the handling of missing data will be explored.

6.2 Description of analysis sets, Part 1

All enrolled patients with available data will be used in the analyses described below.

6.3 Methods of statistical analysis, Part 1

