1.2 Rationale

This PRO validation study will provide the empirical evidence for selecting the primary and secondary endpoints and measures for the planned phase IIB and III development program for AZD3355, in partial responders to PPI treatment with persistent GERD symptoms.

The target patient population for the future AZD3355 program are patients who experience at least moderate intensity GERD symptoms on at least 3 of the past 7 days. However, the study population in the validation protocol also will comprise patients who experience mild symptom intensity. A broader group of patients is being evaluated in the current study to support the identification and validation of symptom clusters in the target patient population.

The information obtained from this study will establish which modifications in the PRO instruments are relevant for both assessment of GERD symptoms and impact of GERD symptoms on patients' lives in the target patient population. Subsequently, the relevant measurement properties of the modified RDQ e-diary and the modified QOLRAD will be established in the target patient population. Additionally, the clinically meaningful change of the modified RDQ e-diary as well as a responder definition will be established.

Once the measurement properties, clinically meaningful change and a responder definition are established with the PRO measures, the remaining AZD3355 clinical development program will utilize these measures in the phase IIB and III studies.

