2. STUDY OBJECTIVES

2.1 Objectives related to validation

- To determine which symptoms in the modified RDQ e-diary are relevant for the target patient population
- To establish the validity, reliability, and ability to detect change (responsiveness) of the modified RDQ e-diary in the target patient population
- To establish the clinically meaningful change of the modified RDQ e-diary in the target patient population
- To determine which symptoms or symptom domains from the modified RDQ e-diary will form the basis for the primary endpoint in future studies in the target patient population
- To determine a responder definition in the target patient population
- To investigate the validity, reliability and ability to detect change (responsiveness) of the modified QOLRAD for assessing the impact of GERD symptoms in the target patient population
- To investigate the validity of alternative diary based PRO instruments for assessing the impact of GERD symptoms in the target patient population

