3.3 Selection of study population

The study population in this study are partial responders to PPI treatment who still experience at least mild intensity GERD symptoms on at least 3 of the past 7 days. Patients will be males and females aged 18 and 70 years, inclusive. The patients must have a history of GERD symptoms for at least 6 months (need not to be consecutive) and must be on optimised^c PPI treatment. Helicobacter pylori serology test will be done at enrolment for baseline characteristics and both Helicobacter pylori positive and negative patients will be included.

Patients who have not responded at all to PPI treatment will not be part of the study population since many of these complete non responders may have other causes for their symptoms other than gastroesophageal reflux. Non-responders to PPI treatment will be excluded based on the evaluation by the investigator.

Patients who still experience GERD symptoms while on PPI therapy continue to have the predominant symptoms of heartburn and regurgitation ([Charbel et al 2005](#), [Mainie et al 2006](#), [Zerbib et al 2006](#)). This was confirmed in a recent set of cognitive interviews and focus groups ([Report from Mapi Values](#)) in patients with GERD symptoms despite PPI treatment.

^c Prior to enrolment, the patients must be continuously treated with an unchanged PPI treatment with doses within the FDA approved label for any GERD indication. The patient must be treated with the PPI for at least 4 weeks prior to enrolment. An optimised PPI treatment is a treatment which according to the investigator's judgment can not be further improved by changing brand or dosing of the PPI during the 4 weeks prior to enrolment. Patients with recently diagnosed reflux (erosive) esophagitis must have completed the prescribed treatment period with up to 8 weeks PPI treatment.

Thus, the selection of patients for the study will be based on the frequency and intensity of the patient-reported symptoms “a burning feeling behind the breastbone” (heartburn) and “unpleasant movement of material upwards from the stomach” (regurgitation).

Patient’s eligibility for Part 1 will be based on symptom frequency and intensity using a 7 day recall report in the modified RDQ screening instrument, whereas eligibility for Part 2 will be based on twice daily symptom recording in the modified RDQ e-diary during the last 7 days of Part 1.

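### Part 1 reliability, convergent/discriminant validity and symptom relevance are analysed only in all enrolled patients (at least mild symptoms), although the objectives are stated for the target population (at least moderate)

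*Protocol*

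**What the plan says.** The protocol's list of definitions separates two populations. Section 3.3 describes the study population as "partial responders to PPI treatment who still experience at least mild intensity GERD symptoms on at least 3 of the past 7 days". Section 1.2 sets the target population higher: "patients who experience at least moderate intensity GERD symptoms on at least 3 of the past 7 days".

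All seven validation objectives in section 2.1 name the target population, for example: "To establish the validity, reliability, and ability to detect change (responsiveness) of the modified RDQ e-diary in the target patient population". Section 1.2 repeats that "the relevant measurement properties of the modified RDQ e-diary and the modified QOLRAD will be established in the target patient population".

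Section 6.2 then sets one analysis set for the whole of Part 1: "All enrolled patients with available data will be used in the analyses described below". Sections 6.3.1 to 6.3.8 define no at-least-moderate subset, either as the main or as a sensitivity analysis. Section 6.3.3 goes further and makes the choice of a new modified QOLRAD factor structure depend on fit in the study population.

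The SAP is announced "for the analyses involving Part 2 data (ie post randomisation data) will be prepared before unblinding of the data", and section 6.4 leaves the Part 2 sets to it. The Part 1 set is therefore settled in the protocol and not deferred.

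**The concern.** An ICC, a Cronbach's alpha or a correlation describes an instrument in a particular population. Each depends on how far patients differ from one another. Adding milder patients tends to widen that spread, so the coefficients tend to be higher than in the at-least-moderate patients for whom they are meant to hold. Symptom frequencies and the most-troublesome-symptom counts can also differ between the two groups.

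Part 1 results have consequences. They decide between mean and maximum as the weekly score (6.3.1) and select the clusters and one of two regurgitation items for Part 2 (6.3.2). They also feed the choice of endpoints for a phase IIB/III programme aimed at the target population (1.2). As planned, no Part 1 statistic answers the reliability, convergent/discriminant validity or symptom-relevance question in that population.

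**Working it through.** **1. Reproduce the plan's own figures (section 6.6).** Inputs: 500 patients in Part 1, 40% stable (k = 200), n = 2 measurements, ICC 0.78 against 0.70, 5% level. The log-F approximation for an ICC test gives:

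- C = [1 + 2(0.70/0.30)] / [1 + 2(0.78/0.22)] = 5.667/8.091 = 0.700, ln C = -0.356.
- Power = Φ(√[(k-1)(n-1)(ln C)²/(2n)] - z) = Φ(√[199 × 0.1268/4] - 1.645) = Φ(2.512 - 1.645) = 80.7%.

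The stated figure of about 80% reproduces as a one-sided test (two-sided gives 71.0%). It uses stable patients from all 500 enrolled. For alpha 0.70 with 2 items and 450 patients, SE = √[2·2/(1·448)] = 0.0945 on the log(1-alpha) scale. The interval is 0.639 to 0.751, which also reproduces the stated ±0.06.

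**2. Effect of restricting to the target population.** The document does not give the share of mild-only patients (q) or the correlation (r) between the severity rule and the score. I assume q = 20-40%, r = 0.3-0.7, normal scores and constant error variance.

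- Variance of the severity variable after cutting off the lowest q: v = 1 + cλ - λ², with c = Φ⁻¹(q) and λ = φ(c)/(1-q). For q = 0.2, v = 0.583. For q = 0.4, v = 0.422.
- Score variance ratio, target to all enrolled: V = 1 - r²(1-v).
- ICC in target = 1 - 0.22/V. Alpha in target = 1 - 0.30/V.

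| q | r | V | ICC (0.78 in all) | alpha (0.70 in all) |
|---|---|---|---|---|
| 20% | 0.3 | 0.963 | 0.771 | 0.688 |
| 20% | 0.5 | 0.896 | 0.754 | 0.665 |
| 20% | 0.7 | 0.796 | 0.724 | 0.623 |
| 40% | 0.3 | 0.948 | 0.768 | 0.684 |
| 40% | 0.5 | 0.856 | 0.743 | 0.649 |
| 40% | 0.7 | 0.717 | 0.693 | 0.582 |

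The ICC drops below 0.75 when V < 0.22/0.25 = 0.88, and below 0.70 when V < 0.22/0.30 = 0.733.

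Starting values matter. Section 4.2.5.1 reports alphas of 0.89 to 0.97 for the original QOLRAD in an earlier sample. An alpha of 0.89 becomes 1 - 0.11/V = 0.85 to 0.89 over the same grid, and 0.97 becomes 0.96 to 0.97.

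A simulation with a fallible severity screen and target shares of 50-80% agrees. An ICC of 0.78 becomes 0.76-0.77, 0.73-0.75 or 0.68-0.72 when the screen correlates 0.4, 0.6 or 0.8 with the true score.

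**3. Precision if the subset is analysed.** The ICC is held at 0.78, one-sided 5%. Alpha is 0.70 with 2 items.

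| Target share | Stable patients | ICC power | Patients for alpha | Alpha interval |
|---|---|---|---|---|
| 100% | 200 | 80.7% | 450 | 0.639 to 0.751 |
| 80% | 160 | 72.6% | 360 | 0.631 to 0.756 |
| 60% | 120 | 61.7% | 270 | 0.619 to 0.764 |

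If the ICC is also lower in the subset, power falls further: at an 80% share and a true ICC of 0.76 it is 49%.

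**The case against.** The strongest reply is that the wider sample is deliberate. Section 1.2 says "A broader group of patients is being evaluated in the current study to support the identification and validation of symptom clusters in the target patient" […]. So validation, and not only discovery, of clusters is part of the stated purpose. That stands as a reason to enrol mild patients and to use them in the factor analysis. It also stands for known-groups validity, which compares three GSRS severity groups and needs the spread. It does not turn coefficients from the wider group into target-population properties, and the same section says those properties will be established in the target population.

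The term is used loosely: section 1.1 describes the target population without a severity level. The list of definitions and section 1.2 are explicit, however. Symptom relevance also draws on the cognitive interviews in section 4.3.1, which are directed at the target population, so Part 1 statistics are not its only support.

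A reader might infer that every validation objective is compromised. The document does not support that. Modified RDQ test-retest, responsiveness and clinically meaningful change are Part 2 analyses whose sets are left to the SAP. The only Part 1 ICC is for the modified QOLRAD, whose objective is to investigate its properties and not to establish them.

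A reader might also infer that the instruments would fail the protocol's cut-offs in later trials. That is not shown either. In section 6.3.5.1, 0.75 divides fair-to-good from excellent reliability and is not a pass mark. In section 6.3.5.2, 0.70 is a recommended minimum with no decision attached. The 0.78 and 0.70 used above are planning inputs, and an alpha that starts exactly at 0.70 falls below it with any shrinkage.

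**Conclusion.** The mismatch holds on the protocol's own defined terms: Part 1 produces no reliability, convergent/discriminant validity or symptom-relevance statistic in the population its objectives name. The expected direction is upward for the modified QOLRAD ICC, the alphas of both instruments and the correlations.

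The size is conditional. It could be negligible (ICC 0.77) if few patients are mild-only or severity is weakly related to the score, as may be so for an impact scale such as the QOLRAD. It could be material (ICC 0.69, alpha 0.58) at the other end of the assumed range. It rests on an assumed mild-only share, constant error variance and normality, whereas the scales are bounded. Confidence is high on the textual conflict and limited on the magnitude. The omission is recoverable, because the data that define the subset are already collected.

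**What to change.** - **Section 6.2:** define a target-population set: at least moderate burning feeling behind the breastbone and/or unpleasant movement of material upwards on at least 3 of 7 days, from data already collected.
- **Modified QOLRAD test-retest (visits 1 to 2):** define the set from the visit 1 screening instrument, or report both the screening and the diary definition. Selecting only on the diary week before visit 2 conditions on one of the two occasions and can itself distort the ICC. The visit 1 rule also selects on one occasion, so agreement between the two definitions is informative.
- **Use of the sets:** report Part 1 reliability, convergent/discriminant validity and symptom-pattern results in the target set as the basis for target-population conclusions. Keep all enrolled patients for factor analysis, known-groups validity and supportive results.
- **Section 6.3.3:** align the study-population wording with the population intended.
- **Section 6.6:** state an expected target share and restate ICC power and alpha precision for it, without enrolling more patients.

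The programming cost is one set definition and repeat runs. The statistical cost is real: ICC power drops from about 81% to about 73% or 62% at shares of 80% or 60%, below the 80% now quoted, even if the ICC is unchanged. The alpha intervals widen only slightly. The Part 2 analysis sets are for the SAP and need no change under this point.

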6.3.1 Calculation of variables, modified RDQ e-diary

In the statistical analysis, the sequences of observations consisting of modified RDQ morning and evening e-diary registrations will be imputed separately according to the following rules. If a single observation is missing, the missing value will be replaced by the larger (more intense) of the two surrounding values. If two or more consecutive observations are missing the values will remain missing. Values for a *day* (24 h period) will then be constructed using the imputed evening and morning registrations. A day will consist of the evening and the following morning registration. Hence, the day denoted in the following sections as the last day prior to visit 2, will consist of the evening before visit 2 and the morning of visit 2. The symptom intensity for a day is defined as the maximum of the two registrations. If either the morning or the evening registration is missing, the corresponding day will be set to missing.

The symptom cluster intensity for a day will be defined as the mean symptom intensity of the items that form the cluster.

When calculating item and symptom cluster scores for a week, either the mean or the maximum value of the daily intensities during the week could be used. In order to decide which definition to use throughout the study, both will be calculated for a symptom cluster consisting of the modified RDQ symptom items a burning feeling behind the breastbone, heartburn, unpleasant movement of material upwards from the stomach, an acid taste in the

mouth, a bitter taste in your mouth and stomach contents (liquid or food) moving upwards to your throat or mouth (ie the modified RDQ items that the modified QOLRAD questionnaire instruction refer to as heartburn or regurgitation), using e-diary registrations the last 7 days prior to visit 2. Those two symptom cluster scores will then be related to the dimension scores of the modified QOLRAD, using responses at visit 2 for the QOLRAD dimensions Emotional distress, Food/drink problems and Sleep disturbance as described in section 4.2.5.1. When relating to Sleep disturbance, only morning e-diary registrations will be used. If one of the definitions for a weekly score clearly reflects the symptom burden more efficiently, that definition will be used in the study. Else the mean intensity over the week will be used.

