Visit 2. (Day 1) Additional PRO instruments (see Table 3) will be completed by all patients prior to any further assessment. The modified RDQ e-diary registrations during the last 7 days will be used to evaluate if the patient meets the criteria for being randomised into Part 2.

For each eligible patient the investigator will check the laboratory results of serum creatinine, AST, ALT, potassium, magnesium and other serum electrolytes from visit 1. Women of childbearing potential will undergo a second urine pregnancy test.

If scheduled, the first cognitive interview will be performed at visit 2 (with a time window of 5 days prior to visit 2). When an interview is conducted on the day of visit 2, then the interview will be carried out after the completion of the PRO instruments, and prior to clinical assessments.

Patients still eligible for the study will then undergo a physical examination, weight and a laboratory screen. Further, an e-diary device check (eg, battery status, data transfer) and e-diary compliance review will be done.

Prior to the first dose of investigational product, a dECG will be performed followed by the measurement of a supine and standing BP and pulse. The patients fulfilling all of the randomisation criteria will then be randomised to either placebo or AZD3355 treatment 65 mg bid for 4 weeks in the proportion 1:1. The patient will then take the first dose of the investigational product at the site. One hour after the first dose a dECG will be performed again, followed by the measurement of a supine and standing BP and pulse.

Investigational product will be dispensed at the visit sufficient for treatment until visit 4. The patients will be instructed to take 1 capsule in the morning after symptom registration in the e-diary but approximately 30 minutes before breakfast and 1 capsule in the evening approximately 30 minutes before their main meal, with a glass of water. Rescue medication (GELUSIL[®] antacid/anti-gas tablets) could still be used if necessary.

The patients will also be instructed to bring any empty bottles, cartons and/or blister packs, as well as any unused investigational products and rescue medication, with them to visit 4.

ePRO data collection during Part 2

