Randomised patients will continue twice daily e-diary recordings of GERD symptoms, impact of symptoms and use of GELUSIL[®] antacid/anti-gas tablets until the morning on the day of visit 5. The study staff will continue the regularly monitoring of the e-diary compliance as during Part 1.

Visit 3 (phone visit). 5 to 9 days after randomisation, the study staff at the clinic will phone the patient, ask about drug compliance and discuss the e-diary device and e-diary compliance.

Visit 4. 12 to 16 days after randomisation, patients should complete additional PRO instruments prior to any further assessment (see [Table 1](#)), dECG, supine and standing BP and pulse, laboratory screen, e-diary device check and e-diary compliance review and drug accountability. Drug will be dispensed for the last two treatment weeks. A second carton of rescue medication (GELUSIL[®] antacid/anti-gas tablets) will be dispensed for continued use as necessary.

The patients will also be instructed to bring any empty bottles, cartons and/or blister packs, as well as any unused investigational products and rescue medication, with them to visit 5.

Visit 5. 26 to 30 days after randomisation, patients should complete additional PRO instruments (see [Table 3](#)) prior to any further assessment, physical examination, weight, dECG, supine and standing BP and pulse, laboratory screen, e-diary device check and e-diary compliance review and drug accountability. The patient will take the last dose of study drug the evening before the day of visit 5, the optimised PPI treatment will continue. The e-diary recordings of symptoms will end in the morning the day of visit 5 and the e-diary device will be collected at the site.

The patients will be instructed to bring any empty GELUSIL[®] antacid/anti-gas tablets cartons and/or blister packs, as well as any unused rescue medication, with them to visit 6.

If scheduled, the second cognitive interview will be performed at visit 5 (with a time window of up to 7 days prior to or 2 days after visit 5). When an interview is conducted on the day of visit 5, then the interview will be carried out after the completion of the PRO instruments, and prior to clinical assessments.

Visit 6. 12-16 days after visit 5, a follow up visit is done. Each patient will undergo a physical examination, an extended laboratory screen, dECG, supine and standing BP and pulse. Women of childbearing potential will undergo a urine pregnancy test.

Figure 2 Study flow chart

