4.2.13 Administration of PRO instruments

The PRO instruments are to be self-administered and the patients will be asked to complete the PRO questionnaires and questions in electronic format using hand-held electronic devices. When completing PRO instruments at visits, patients will use a site-based electronic device. For the twice daily registrations of the modified RDQ e-diary and the Impact of Symptoms e-diary items, patients will use a home-based electronic device (e-diary device). The site-based and home-based devices will be of the same type.

At study visits, the PRO questionnaires and questions will be completed as described in [Table 3](#) and will automatically appear on the screen of the site-based electronic device, when the site staff selects the appropriate visit in the device.

The PRO questionnaires and questions for the twice daily e-diary recordings will be automatically appear on the screen of the e-diary device in the order listed in [Table 4](#), when the patient activates the bedtime and morning reports, respectively. Patient will be asked to complete the bedtime report just prior to bedtime in the evening, and the morning report upon waking up in the morning. The bedtime report will be available daily from 8:00 pm until 2:00 am the next day, for completion by the patient. There will be a reminder alarm at 11:00 pm if the subject has not yet completed the bedtime report at that time. The morning report will be available daily from 05:00 am until 11:00 am, for completion by the patient. The patient will

be asked to set a flexible wakeup alarm after completion of the bedtime report, to be used as a reminder for the completion of the morning report.

Standard procedures for minimising bias and enhancing ePRO compliance will be followed throughout the study.

The patients will be instructed to complete all questionnaires and questions independently, at study visits as well as when completing the e-diary questions, so that the responses reflected the patient's own perception. Each site will have a designated quiet space for patients to use when completing the PRO instruments at the study visits.

Dedicated study staff at each site will be responsible for ensuring that the ePRO process will be followed according to the specific instructions from the clinical study team and the ePRO provider. A detailed manual, which covers the description of the ePRO solution and practical issues that may arise, will be provided to the study staff.

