6.5.3 Clinically meaningful change (CMC)

Anchor based approach

Patients will be classified into sub groups based on their response to the OTE assessment at the visit after the 4 weeks treatment period. The following potential definitions of a clinically meaningful change will be derived and evaluated:

- An inpatient change from the last 7 days before first dose to the last 7 days of treatment with respect to the number of days with symptoms, below the median change observed in the subgroup of patients classified as “Moderately better” by the OTE.
- An inpatient change from the last 7 days before first dose to the last 7 days of treatment with respect to the number of days with symptoms, below the 25th quantile and the 10th quantile of the change observed in the subgroup of patients classified as “Unchanged” by the OTE.

Further details and additional potential anchor based definitions of clinically meaningful change will be given in the SAP.

The cumulative proportion of patients by the change in the number of days with symptoms, as defined above, will be presented by OTE classification.

Distribution based approach

The following potential definitions of a clinically meaningful change will be derived and evaluated:

- Having number of days with symptoms during the last 7 days of treatment less than the 10th quantile and the 5th quantile of the number of days with symptoms during the last 7 days before first dose.

Further details and additional potential distribution based definitions of clinically meaningful change will be given in the SAP.

Details on how to handle missing data will be given in the SAP.

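### The single-gap diary rule has no stop at visit 2, so a few entries made after the first dose can enter the baseline week; the effect is small and one sentence removes it

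*Protocol*

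**What the plan says.** Protocol section 6.3.1 states that "the sequences of observations consisting of modified RDQ morning and evening e-diary registrations will be imputed separately according to the following rules". For a lone gap: "If a single observation is missing, the missing value will be replaced by the larger (more intense) of the two surrounding values". For longer gaps: "If two or more consecutive observations are missing the values will remain missing". A day pairs an evening with the following morning, takes the larger of the two ratings, and is missing if either is missing after imputation. The last day before visit 2 "will consist of the evening before visit 2 and the morning of visit 2".

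Section 3.1 places randomisation and dosing within that visit: "The patient will then take the first dose of the investigational product at the site". Recording then goes on without a break: "Randomised patients will continue twice daily e-diary recordings of GERD symptoms", up to the morning of visit 5. Section 4.2.13 fixes the evening window: "The bedtime report will be available daily from 8:00 pm until 2:00 am the next day". The evening entry of visit 2 therefore normally follows the on-site dose.

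The week before visit 2 is used in sections 6.3.1 (choice of weekly mean or maximum), 6.3.2 (factor analysis), 6.3.5.2 (Cronbach's alpha), 6.3.6 (construct validity) and 6.5.1 (visit 2 score for test-retest). Section 6.5.3 uses the same week as the baseline for clinically meaningful change ("An inpatient change from the last 7 days before first dose to the last 7 days of treatment") but leaves missing-data handling for that analysis to the SAP.

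**The concern.** A week defined as lying before visit 2 should contain only what the patient recorded before visit 2. Because each series runs on past the visit and no cut is stated, the later neighbour of the last evening or last morning is a post-dose rating. Taking the larger of the two neighbours lets that rating decide the filled value whenever it is the worse one.

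The rule also works unevenly within one analysis set. Part 1 uses all enrolled patients, about 500, of whom about 450 are expected to be randomised. The same boundary gap is filled in the 450. The rule gives no value for the other 50 or so, who have no later entry. What is at stake is whether the Part 1 measurement properties and the visit 2 test-retest score rest on pre-treatment data handled alike for everyone.

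**Working it through.** The plan gives no figure to reproduce, so the check has four steps.

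**1. Which entries are exposed.** Call visit 2 day 0. The baseline week holds evenings -7 to -1 and mornings -6 to 0, which makes 14 registrations. With the series kept separate:

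- Evening -1: the later neighbour is evening 0, after the on-site dose.
- Morning 0: the later neighbour is morning +1, after the on-site dose.
- The other 12 have a later neighbour before the dose.

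So 2 of 14 registrations are exposed, both in the last baseline day. If the series were interleaved instead, 1 of 14 (morning 0) would still be exposed.

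**2. How often the fill happens.** The protocol states no miss rate, so p per entry is an assumption, with misses independent. A lone gap needs the entry missing and both neighbours present:

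P(one entry) = p(1 - p)^2; P(at least one of two) = 1 - [1 - p(1 - p)^2]^2.

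| p | P(one entry) | P(at least one) | of 450 |
|---|---|---|---|
| 5% | 0.05 x 0.9025 = 0.0451 | 8.8% | about 40 |
| 10% | 0.10 x 0.81 = 0.0810 | 15.5% | about 70 |
| 15% | 0.15 x 0.7225 = 0.1084 | 20.5% | about 92 |

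If compliance varies between patients (beta-distributed miss rates, concentration 5), simulation gives about 6%, 11% and 15%.

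**3. How often the baseline changes.** A fill alters the result only if the post-dose rating exceeds the pre-dose neighbour and also exceeds the other rating of the same day, because the day takes the maximum. This was simulated under assumed inputs: ratings 0 to 5, mean 2, SD 1.3, within-patient correlation 0.3 to 0.7, no drug effect, independent misses. The rule as written was compared with carrying the preceding same-time entry.

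| p | last-day score changed | symptom-day count changed | weekly mean, average shift |
|---|---|---|---|
| 5% | 1.5% to 1.9% | about 0.2% | 0.003 to 0.004 |
| 10% | 2.6% to 3.5% | about 0.3% | 0.004 to 0.007 |
| 15% | 3.5% to 4.5% | 0.4% to 0.5% | 0.006 to 0.010 |

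Among patients whose weekly mean changes, it moves by about 0.16 to 0.22 points. The ceiling for one patient is 5/7 = 0.71 points, or one symptom day of seven. That ceiling holds for the weekly mean only. Section 6.3.1 leaves the weekly maximum open, and under it one borrowed rating could set the whole weekly score.

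**4. Cost of leaving the boundary gap missing.** Section 6.3.2 sets the weekly score to missing when two or more of the seven days are missing. Under the same assumptions, the share with a missing baseline rises by about 0.05, 0.25 and 0.65 percentage points at 5%, 10% and 15% missed entries.

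**The case against.** The strongest reply is context. Section 6.3.1 stands under the Part 1 methods, and section 6.1 identifies Part 2 data with post-randomisation data and reserves analyses of them for the SAP. On that reading a Part 1 series simply stops at visit 2. This is a fair reading, but the text does not say so. If it is meant, the last evening and last morning have only one neighbour, and a rule that needs two gives no answer. Either reading calls for a sentence.

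The reply also limits the consequences, and these limits stand. A reader might infer four stronger things that the protocol does not support:

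- **Eligibility is affected.** It is not. Section 6.3.1 governs the statistical analysis. Entry to Part 2 is decided at visit 2 by a separate algorithm, before any later entry exists.
- **Baseline shares error with follow-up.** The borrowed entry is from the evening of visit 2 or the next morning. Visit 4 falls 12 to 16 days after randomisation, so its 7-day window opens at about day 5 (12 - 7) at the earliest; the visit 5 window is later still. Overlap could arise only in a patient who stops within roughly the first week.
- **The arms are biased against each other.** Section 6 states no efficacy comparison between arms. Effect sizes and clinically meaningful change are grouped by OTE response.
- **Clinically meaningful change is compromised.** Section 6.5.3 leaves its missing-data handling to the SAP, so that use is open rather than fixed wrongly.

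The diary also has a bedtime reminder, a wake-up alarm and daily compliance checks, which may hold misses down, although no rate is given.

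**Conclusion.** The point holds as a minor one. As written, 2 of 14 baseline registrations in randomised patients can take a post-dose value, and the same gap has no defined fill in patients who are not randomised. The uses that rely on this text without a stated deferral are the Part 1 factor, alpha and validity analyses, the choice of weekly mean or maximum, and the visit 2 test-retest score.

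The 9% to 20% figure counts fills, not altered baselines, and a reader should not take it as the size of the problem. The last-day score changes in about 1.5% to 4.5% of randomised patients and the weekly mean shifts by less than 0.01 on average. These figures rest on assumed miss rates, independent misses and an assumed rating distribution. The exposure of the two entries rests on the text alone.

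**What to change.** Add to section 6.3.1 that, for the baseline week, each imputation sequence ends at the last registration before the first dose. State what happens to a gap in the last evening or last morning entry: either use pre-dose entries only (for example, carry the preceding same-time entry) or leave it missing. Apply the same rule to randomised and non-randomised patients. No change to the eligibility algorithm is needed.

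The cost is one sentence and the matching programming. If the gap is left missing, the share of patients without a baseline score rises by under 1 percentage point at up to 15% missed entries.
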